#### 11.5. Data security

UoB has policies in place, which are designed to protect the security, accuracy, integrity and confidentiality of Personal Data. The trial will be registered with the Data Protection Officer at UoB and will hold data in accordance with the Data Protection Act (2018 and subsequent amendments). The Trial Office has arrangements in place for the secure storage and processing of the trial data which comply with UoB policies.

The Trial Database System incorporates the following security countermeasures:

Physical security measures: restricted access to the building, supervised onsite repairs and storages of back-up tapes/disks are stored in a fire-proof safe.

Logical measures for access control and privilege management: including restricted accessibility, access controlled servers, separate controls of non-identifiable data.

Network security measures: including site firewalls, antivirus software and separate secure network protected hosting.

System management: the system will be developed by the Programming Team at the Trial Office, and will be implemented and maintained by the Programming Team

System design: the system will comprise of a database and a data entry application with firewalls, restricted access, encryption and role based security controls.

Operational processes: the data will be processed and stored within BCTU

System audit: The system will benefit from the following internal/external audit arrangements:

- Internal audit of the system
- Periodic IT risk assessment

Data Protection Registration: UoB's Data Protection Registration number is Z6195856.

### 11.6. Archiving

All records created by following trial procedures and all documents listed in guidance relating to the conduct of the trial must be retained and archived for the specified period.

The trial master file (TMF) is composed of a sponsor file, held by the sponsor organisation, and an investigator site file, held by the site investigator. Documents are archived following any regulatory requirements and any local procedures.

It is the responsibility of the PI to ensure all essential trial documentation and source documents (e.g., signed ICFs, Investigator Site Files, Pharmacy Files, participants' hospital notes, copies of CRFs) at their site are securely retained for the contractual period. Archiving will be authorised by BCTU on behalf of UoB following submission of the end of trial report. No documents should be destroyed without prior approval from the BCTU Director or their delegate.

The TMF will be stored at BCTU for at least 3 years after the end of the trial. Long-term offsite data archiving facilities will be considered for storage after this time; UNiTY trial data will be stored securely and confidentially for at least 10 years (acknowledging that participant medical records will be stored for 50 years as standard under HFEA). BCTU has standard processes for both hard copy and computer database legacy archiving.

## 12.QUALITY CONTROL AND QUALITY ASSURANCE

## 12.1. Site set-up and initiation

All PIs will be asked to sign the necessary agreements including a Site Signature and Delegation log between the PI and the Trial Office and supply a current CV and GCP certificate. All members of the site research team are required to sign the Site Signature and Delegation Log, which details which tasks have been delegated to them by the PI. The Site Signature and Delegation Log should be kept up to date by the PI. It is the PI's responsibility to inform the Trial Office of any changes in the site research team.

Prior to commencing recruitment, each recruiting site will undergo a process of site initiation, either a meeting or a teleconference, at which key members of the site research team are required to attend, covering aspects of the trial design, protocol procedures, adverse event reporting, collection and reporting of data and record keeping. Sites will be provided with an ISF containing essential documentation, instructions, and other documentation required for the conduct of the trial.

#### 12.2. Monitoring

The central and on-site monitoring requirements for this trial have been developed in conjunction with the trial specific risk assessment and are documented in the trial specific monitoring plan.

#### 12.2.1. On-site monitoring

For this trial, all sites will be monitored in accordance with the trial risk assessment and monitoring plan. Any monitoring activities will be reported to the Trial Office and any issues noted will be followed up to resolution. Additional on-site monitoring visits may be triggered. PIs and site research teams will allow the UNITY trial staff access to source documents as requested. The monitoring will be conducted by BCTU/UoB staff.

## 12.2.2. Central monitoring

The Trial Office will check received ICFs and CRFs for compliance with the protocol, data consistency, missing data and timing at a frequency and intensity determined by the Data Management Plan. Sites will be sent requests for missing data or clarification of inconsistencies or discrepancies.

## 12.3. Audit and inspection

The Investigator will permit trial-related monitoring, audits, ethical review, and regulatory inspection(s) at their site and provide direct access to source data/documents. The investigator will comply with these visits and any required follow-up. Sites are also requested to notify the Trial Office of any relevant inspections or local audits.

## 12.4. Notification of Serious Breaches

The sponsor is responsible for notifying the REC of any serious breach of the conditions and principles of GCP in connection with that trial or of the protocol relating to that trial. Sites are therefore requested to notify the Trial Office of any suspected trial-related serious breach of GCP and/or the trial protocol as soon as they become aware of them. Where the Trial Office is investigating whether or not a serious breach has occurred, sites are also requested to co-operate with the Trial Office in providing sufficient information to report the breach to the REC where required and in undertaking any corrective and/or preventive action.

Sites may be suspended from further recruitment in the event of serious and persistent non-compliance with the protocol and/or GCP, and/or poor recruitment.

### **13.END OF TRIAL DEFINITION**

The end of trial will be the date of the last data capture including resolution of queries. This includes the capturing of all qualitative data and lab results in the UNiTY sub-studies. This will allow sufficient time for the completion of protocol procedures, data collection and input and data cleaning. The Trial Office will notify the REC and the Sponsor within 90 days of the end of trial. Where the trial has been terminated early, the Trial Office will notify the REC within 15 days of the end of trial. The Trial Office will provide the REC and the Sponsor with a summary of the clinical trial report within 12 months of the end of trial.

## 14.STATISTICAL CONSIDERATIONS

## 14.1. Sample size

The HFEA suggests that the primary outcome rate in the IVF group will be approximately 28% (1). To ensure the IUI group will be within a 10% margin of non-inferiority (i.e., no lower than 18%) with 90% power (one-sided alpha of 0.025, equivalent to a two-sided alpha of 0.05), the trial will require 942 participants (assuming a conservative 10% loss to follow-up).

A three IUI cycle rate of at least 18% (approximately 6.4% per-cycle) would deliver 64% of the live births of IVF for 46% of the total costs, justifying the 10% margin of non-inferiority from a commissioning or self-funding couple financial perspective (see Table 8*Table 8*). A success rate matching IVF (28%) would be for 44% of the total costs of IVF (see Table 9).

The margin of non-inferiority is also justifiable if we consider that many of those allocated to IUI who do not achieve live birth will go on to receive an IVF cycle provided by the NHS, even considering further interventions and the possibility of natural birth in the IVF policy group [MRC/NIHR framework, core element 1: context]. We will assess whether the initial IUI treatment policy is the superior approach in our medium-term assessment (25 months post-randomisation). For this assessment, we will have adequate (>80%) power to detect a 10% difference in live birth (≥34 weeks) rates (e.g., 45% vs 35%).

**Table 7:** Cost comparison, assuming a 10% margin of inferiority, between 3 cycles of IUI (assumed success rate per cycle of 6.4%) and 1 cycle of IVF (assumed success rate per cycle of 28%)

	IUI Cycle 1	IUI Cycle 2	IUI Cycle 3	IVF Cycle 1
Number of couples	100.0	89.6	80.4	100.0
Expected live births	6.4	6.0	5.6	28.0
		Total live births	18.0	28.0
		Number of cycles	281.2	100.0
	Cost per cycl		£605.33	£3,682.00
	Total cost		£170,225.54	£368,200.00
	Cost per live birth		£9,458.33	£13,150.00

**Table 8:** Cost comparison, assuming a 0% margin of inferiority, between 3 cycles of IUI (assumed success rate per cycle of 10.36%) and 1 cycle of IVF (assumed success rate per cycle of 28%)

	IUI Cycle 1	IUI Cycle 2	IUI Cycle 3	IVF Cycle 1
Number of couples	100.0	89.6	80.4	100.0
Expected live births	10.4	9.3	8.3	28.0
		Total live births	28.0	28.0
		Number of cycles	270	100.0
		Cost per cycle	£605.33	£3,682.00
	Total cost		£163,435.94	£368,200.00
	Cost per live birth		£5,842.99	£13,150.00

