### 8.2.2. Secondary outcomes

#### 8.2.2.1. Clinical

#### **Pregnancy outcomes**

The following outcomes will be assessed at two time points: 19 months post-randomisation to allow for pregnancy outcomes to be obtained and concern pregnancies conceived within 270 days (approximately 9 months) of randomisation; and 25 months post-randomisation to allow for pregnancy outcomes to be obtained and concern pregnancies conceived within 450 days (approximately 15 months) of randomisation. This will enable us to determine the medium-term effect of the initial treatment policy decision.

- Singleton live birth ≥37 weeks;
- TTP leading to a live birth defined as time from randomisation to pregnancy in days (censored at 270 days);
- Cycle cancellation and reason (failure to respond / over-response);
- Biochemical pregnancy;
- Clinical pregnancy;
- Ongoing pregnancy at 12 weeks (range 11 to 14 weeks);
- Multiple pregnancy;
- Ectopic pregnancy;
- Miscarriage (defined as delivery before 24 weeks of gestation);
- Stillbirth (defined as intrauterine death ≥24 weeks);
- Termination:
- Number of embryos remaining (IVF group).

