#### 14.2. Analysis of outcomes

A separate Statistical Analysis Plan will be produced and will provide a more comprehensive description of the planned statistical analyses. A brief outline of the planned analyses is given below.

The primary comparison groups will be composed of those randomised to receive three cycles of letrozole stimulated IUI versus those randomised to receive one cycle of IVF. For all outcomes, analyses will be based on the intention to treat principle, i.e. all participants will be analysed in the treatment group to which they were randomised irrespective of compliance or other protocol deviation (see Table 10 for proposed populations). For the primary outcome, given the nature of the non-inferiority design, supportive per-protocol and Complier Average Causal Effect (CACE) analyses (38) will be considered alongside the intention-to-treat population. All outcomes will be adjusted for the minimisation variables listed in Section 6.4.2 where possible.

For all major outcome measures, summary statistics and differences between groups, e.g. risk difference, relative risks, will be presented with 95% confidence intervals. For the primary outcome, this is equivalent to a one-sided 97.5% confidence interval and hence conservative in terms of the non-inferiority margin. For the trial to declare non-inferiority of the three cycles of letrozole stimulated IUI method, the lower margin of the absolute risk difference (see 14.2.1 for calculation method) confidence interval must not exceed 10%.

All secondary outcomes will be considered as exploratory; no adjustment for multiple comparisons will be made and hence significance should not be inferred from the confidence interval width.

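### Section 14.1 promises a powered superiority assessment of live birth ≥34 weeks at 25 months, but section 8.2 does not list that outcome and section 14.2 makes it exploratory

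*Protocol*

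**What the plan says.** Section 14.1, after setting the non-inferiority sample size, turns to the medium term: "We will assess whether the initial IUI treatment policy is the superior approach in our medium-term assessment (25 months post-randomisation". It adds that "we will have adequate (>80%) power to detect a 10% difference in live birth (≥34 weeks) rates", with 45% against 35% as the example. It gives no significance level for this comparison and does not say which arm has which rate.

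Section 8.2.1 defines live birth ≥34 weeks for conceptions within 270 days only, assessed at 19 months. Section 8.2.2.1 lists the outcomes assessed at both 19 and 25 months, the latter covering conceptions within 450 days. The only live-birth rate in that list is "Singleton live birth ≥37 weeks". The list also has time to pregnancy leading to a live birth (censored at 270 days). A second list describes births at or beyond 24 weeks, with gestation cut-offs at 28, 32 and 37 weeks but none at 34.

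The 450-day version does appear in Table 9, which sets out analysis populations for live birth ≥34 weeks with a medium-term block.

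On inference, section 14.2.2 places the 25-month assessment among the secondary outcomes. Section 14.2 says "All secondary outcomes will be considered as exploratory; no adjustment for multiple comparisons will be made and hence significance should not be inferred", and the sentence closes by naming the width of the confidence interval as what should not be read that way. No exception is made.

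**The concern.** Power to detect a difference presupposes a test at a set level and a conclusion drawn from it. Section 14.1 offers both for the 25-month comparison, and section 14.2 withdraws them. The outcome on which the promise rests is also missing from the section where a reader looks up what the trial measures.

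The comparison matters. Section 1.1.4 expects every couple unsuccessful after three IUI cycles to go on to at least one IVF cycle. The 25-month result is therefore the one that speaks to the policy of IUI first, then IVF, against IVF first. If the text stays as it is, a clear result at 25 months meets two rules that point in opposite directions, and the choice between them would be made after the data are in. Section 14.3 holds the primary analysis until 25-month follow-up is complete, so both results would be in hand when that choice was made.

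**Working it through.** **Inputs, all from section 14.1 unless noted**
- IVF rate for the primary outcome: "the primary outcome rate in the IVF group will be approximately 28" per cent.
- Margin and power: "within a 10% margin of non-inferiority (i.e., no lower than 18%) with 90% power".
- Level: "one-sided alpha of 0.025, equivalent to a two-sided alpha of 0.05". This is stated for the primary outcome; I assume two-sided 5% for the 25-month comparison.
- Size: "the trial will require 942 participants (assuming a conservative 10% loss to follow-up"; 471 per arm (Trial Summary).
- Medium-term rates: 45% and 35%.

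**1. The plan's sample size**

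n per arm = (1.960 + 1.282)² × 2 × 0.28 × 0.72 / 0.10² ≈ 423.7, so 424. Total 848; 848 / 0.90 = 942.2. The stated 942 reproduces to rounding. Analysed per arm: 471 × 0.90 = 423.9, about 424.

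**2. The plan's medium-term power**

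SE = √[(0.45 × 0.55 + 0.35 × 0.65) / 424] = √(0.475 / 424) = 0.03347

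Power = Φ(0.10 / 0.03347 − 1.960) = Φ(1.028) = 84.8%

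| Variant | Power |
|---|---|
| 424 per arm, unpooled variance | 84.8% |
| 424 per arm, pooled variance under the null | 84.6% |
| 424 per arm, continuity-corrected | 82.8% |
| 471 per arm (no loss), pooled | 88.1% |

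All exceed 80%, so the statement in section 14.1 is numerically correct. If the level were instead split equally with one other test (two-sided 2.5%, an assumption), power at 424 per arm would be 76.9%, below the claim. The claim therefore depends on a level that the protocol does not state.

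**3. The texts side by side**

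| Question | Sections 8.2.1, 8.2.2.1 | Section 14.1 | Sections 14.2, 14.2.2 | Table 9 |
|---|---|---|---|---|
| Live birth ≥34 weeks at 450 days / 25 months present? | No | Yes | Only as the general 25-month assessment | Yes |
| Status | Not listed | Superiority, powered | Secondary, exploratory | Population only |
| Superiority test stated? | – | Implied, no level | No | – |

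Section 14.2.2 analyses binary secondary outcomes by the primary method, and the only p-value described for that method (section 14.2.1) belongs to the non-inferiority hypothesis.

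**4. What a gate on the primary result would cost**

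If superiority at 25 months were tested only after 9-month non-inferiority is shown, the chance that the gate opens, with 424 per arm, is:
- True rates 28% and 28%: SE = √(2 × 0.2016 / 424) = 0.03084; Φ(0.10 / 0.03084 − 1.960) = Φ(1.283) = 90%.
- True rates 25% (IUI) and 28% (IVF), an illustrative assumption: SE = √[(0.1875 + 0.2016) / 424] = 0.03029; Φ(0.07 / 0.03029 − 1.960) = Φ(0.351) = 64%.

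The chance of passing both tests cannot exceed the smaller of the gate probability and 84.8%. In the first case it lies between 0.90 + 0.848 − 1 = 75% and 84.8%. In the second it is at most 64%.

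**The case against.** The strongest reply is that most of the comparison is already fixed in advance. Section 14.1 names the outcome, time point and example rates. Table 9 gives its populations, section 14.2.2 the model, objective 6 in section 2.2.1 the aim, and the schedule of assessments the data collection. This stands. A reader might infer that the outcome is unspecified, or that any later claim would be wholly post hoc. The documents do not support that: what is missing is an entry in the outcome list and one agreed inferential status.

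A reader might also infer that the 10-point margin depends on this test. It does not. Section 14.1 justifies the margin by cost, then by the fact that many couples in the IUI arm will go on to IVF. The superiority sentence follows as a separate statement.

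Nor does the text reduce the comparison's power to nothing. The estimate and its 95% interval would still be reported, and the power figure still says something about precision.

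Finally, it can be said that the verb in section 14.1 promises only an assessment, and that testing order usually sits in the SAP. The second half is fair for detail. But here the protocol itself states two incompatible positions, and a rule covering all secondary outcomes leaves the SAP no room to pick one without contradicting the other. If only estimation was meant, the language of superiority and of power to detect is the wrong wording.

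**Conclusion.** The inconsistency is real and lies in the protocol's own text: a superiority assessment with a correct power of about 85% (424 per arm, 45% against 35%, two-sided 5% assumed) is classed as exploratory, and its outcome is absent from section 8.2. It is a fault of specification and inference, not of arithmetic. Resolving it decides whether the trial may conclude that IUI first is superior at 25 months. It leaves the primary outcome, the 942 couples and the non-inferiority conclusion as they are. It does not follow that the comparison must be made confirmatory, or that it must be gated on the primary result; both are choices for the sponsor.

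**What to change.** 1. Add to section 8.2.2.1: live birth at ≥34 weeks from a conception in the first 450 days after randomisation, assessed at 25 months.
2. Before any comparison of outcomes by arm is seen, reconcile sections 14.1 and 14.2 by one of two routes:
   - **Confirmatory.** Name it the single key secondary outcome, exempt it from the exploratory sentence, and state a two-sided 5% superiority test and its place relative to the primary test. All other secondary outcomes stay exploratory.
   - **Exploratory.** Reword section 14.1 as estimation with a 95% confidence interval and no superiority conclusion.
3. If the confirmatory route uses a fixed sequence after primary non-inferiority, say that it costs no alpha but lowers the chance of a claim below the stand-alone 85%. The gate opens about 90% of the time only if the true 9-month rates are equal, and about 64% of the time at 25% against 28%. The sequence can therefore block the 25-month claim when IUI is somewhat behind at 9 months and recovers after IVF.

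Cost: a few sentences in a protocol amendment, carried into the SAP. No extra couples, visits or data.

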#### 14.2. Analysis of outcomes

A separate Statistical Analysis Plan will be produced and will provide a more comprehensive description of the planned statistical analyses. A brief outline of the planned analyses is given below.

The primary comparison groups will be composed of those randomised to receive three cycles of letrozole stimulated IUI versus those randomised to receive one cycle of IVF. For all outcomes, analyses will be based on the intention to treat principle, i.e. all participants will be analysed in the treatment group to which they were randomised irrespective of compliance or other protocol deviation (see Table 10 for proposed populations). For the primary outcome, given the nature of the non-inferiority design, supportive per-protocol and Complier Average Causal Effect (CACE) analyses (38) will be considered alongside the intention-to-treat population. All outcomes will be adjusted for the minimisation variables listed in Section 6.4.2 where possible.

For all major outcome measures, summary statistics and differences between groups, e.g. risk difference, relative risks, will be presented with 95% confidence intervals. For the primary outcome, this is equivalent to a one-sided 97.5% confidence interval and hence conservative in terms of the non-inferiority margin. For the trial to declare non-inferiority of the three cycles of letrozole stimulated IUI method, the lower margin of the absolute risk difference (see 14.2.1 for calculation method) confidence interval must not exceed 10%.

All secondary outcomes will be considered as exploratory; no adjustment for multiple comparisons will be made and hence significance should not be inferred from the confidence interval width.

### **14.2.1.** Primary outcome

The primary outcome is a binary outcome, and we will use a mixed effect binomial regression model to estimate an absolute risk difference between groups and 95% confidence interval (primary method). Relative risks will be calculated in a similar fashion using a log-binomial regression model. Parameters for treatment group as well as the minimisation variables (listed in Section 6.4.2 will be included in the model as fixed effects (apart from randomising centre which will be included as a random effect). The p-value (relating to the non-inferiority hypothesis) as generated by the model estimating the absolute risk difference will be presented.

### 14.2.2. Secondary outcomes

The secondary outcomes that are binary (i.e., yes/no) will be analysed using the same methods as described for the primary outcome (see Section 14.2.1), with corresponding 95% confidence intervals (this includes the longer-term assessment at 25 months). For those secondary outcomes that are continuous (e.g. Gestational age at delivery, Birthweight, CSQ-8 score), mixed effects linear regression methods will be utilised to calculate an adjusted mean difference and 95% confidence interval. Time-to-event outcomes (e.g. TTP leading to a live birth) will be analysed using a mixed effects ('frailty') Cox Proportional Hazard model, allowing the same minimisation variables as fixed effects and randomising centre as a random effect. The treatment effect will be expressed as adjusted hazard ratio with 95% confidence interval. Regarding safety, the total number of participants experiencing SAEs will be given by allocation group along with a descriptive table of the events, and statistical significance will be determined by a chi-square test; other safety data including complications will be tabulated by group but are not expected to be formally analysed.

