# Risk

The main risk associated with IVF is ovarian hyperstimulation syndrome (OHSS), which causes ovaries to become enlarged and fluid to leak into the abdomen. When mild this is uncomfortable and interferes with daily activities. However, when severe, patients are at high risk of blood clots and may need to be hospitalised. IVF also involves egg collection, a surgical procedure with the most common risks being bleeding and pelvic infection.

Multiple pregnancy with twins is highly risky for the pregnant partner and the babies, with the HFEA acting via regulation to minimise these occurrences. There are some concerns that the rates of multiple pregnancies may be higher in IUI compared to IVF (single embryo transfer is well-controlled by regulation). However, there is also evidence to say that the numbers are comparable (5).

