# 2.2. Main trial objectives

### 2.2.1. Clinical aims and objectives

The primary objective is to test the hypothesis that in couples with UEI, the policy of offering three cycles of IUI is not substantially worse than the policy of offering IVF by up to a 10% margin of non-inferiority in terms of live birth \ge 34 weeks [MRC/NIHR framework, core element 4: uncertainties].

The secondary clinical objectives for the trial are:

- 1. To evaluate the rates of pregnancy loss for IUI versus IVF for couples with UEI.
- 2. To compare the health of babies born as a result of IUI versus IVF to couples with UEI.
- 3. To compare the complication rates of the two treatment arms.
- 4. To evaluate the TTP leading to a live birth for IUI versus IVF for couples with UEI.
- 5. To explore patient satisfaction in the two treatment arms.
- 6. To compare outcomes of couples over a longer period of 25 months post-randomisation when further interventions may have been provided.
- 7. To explore the different clinical features of IUI and IVF cycles.
- 8. To explore the reasons patients may not complete the full course of treatment or wish for different treatment options.

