## **Complications**

The following outcomes will be assessed:

i.) for the first IVF treatment within 450 days post randomisation for a period of 60 days following the date of FSH injection;

- ii.) for the first three IUI cycles within 450 days post randomisation for a period of 30 days following the date of ovarian stimulation for partial or cancelled cycles, or date of insemination for complete cycles.
  - Ovarian hyperstimulation syndrome (mild, moderate, severe);
  - Pelvic infection;
  - Bleeding post oocyte retrieval (IVF only);
  - o Admission to High Dependency Unit (HDU)/ Intensive Therapy Unit (ITU), standard ward admission, A&E visit or Outpatient review.

The following outcomes will be assessed at 28 days post birth (or patient's discharge date from hospital whichever is sooner).

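### Complication rates are to be compared between arms, but Section 14.2.2 plans counts only, with no between-arm difference or interval for OHSS and other treatment complications

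*Protocol*

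**What the plan says.** Section 2.2.1 lists as its third secondary clinical objective "To compare the complication rates of the two treatment arms". Section 8.2.2.1, under Complications, lists OHSS in three grades, pelvic infection, bleeding after oocyte retrieval (IVF only), and admissions or visits. IVF is covered "for the first IVF treatment within 450 days post randomisation for a period of 60 days following the date of FSH injection". The first three IUI cycles within 450 days are each covered for 30 days. Section 1.1.2 names OHSS as the main risk of IVF.

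Section 14.2.2 starts with a general rule: "The secondary outcomes that are binary (i.e., yes/no) will be analysed using the same methods as described for the primary outcome", with 95% confidence intervals. For safety it then departs from that rule. For serious adverse events, "statistical significance will be determined by a chi-square test". The remainder is dealt with in one clause: "other safety data including complications will be tabulated by group but are not expected to be formally analysed".

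Section 14.2 adds: "For all major outcome measures, summary statistics and differences between groups, e.g. risk difference, relative risks, will be presented with 95% confidence intervals". It also classes all secondary outcomes as exploratory.

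**The concern.** The objective promises a comparison, and the analysis section chooses not to make one beyond a table. This is a stated choice, not a detail left open for the statistical analysis plan. An analysis plan written to match this text would contain no between-arm estimate for any complication.

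The trial accepts up to 10 points fewer live births under IUI. Cost is the main argument for that margin, but Section 1.1.4 also calls IUI attractive because it carries lower risk. Couples and commissioners who weigh births against harm need the difference in harm and its uncertainty. Rarity does not explain the exemption, because ectopic pregnancy and birth before 28 weeks are also secondary outcomes and do fall under the binary rule.

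**Working it through.** **1. Does another rule supply the estimate?**
- *Major outcome measures (14.2).* The term is not defined, and the clause in 14.2.2 is the specific one for complications.
- *SAE chi-square (14.2.2).* It gives one pooled p-value, with no effect size and nothing specific to OHSS. Section 10.4.2 treats OHSS admission as an expected event reported on the relevant case report forms, and Section 10.3 limits SAE reports to unexpected events. Whether OHSS admissions enter the SAE count is therefore unclear.
- *Binary rule (14.2.2).* It would fit pelvic infection and admission, but the later clause takes complications out of it.

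No other section plans an estimate.

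**2. Plan figures used, reproduced first.**
- Sample size (14.1): 2 × 0.28 × 0.72 × (1.960 + 1.282)² / 0.10² = 423.7 per arm. Divided by 0.9 this is 470.7, so 471 per arm and 942 in total, as stated.
- IUI cycles per couple (cost tables in 14.1): 1 + (1-p) + (1-p)². At p = 0.064 this is 2.812, and at p = 0.1036 it is 2.700, matching 281.2 and 270 per 100 couples.

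**3. What an interval would show.** All event rates and IVF uptake values here are assumptions. Let f be the share of IUI-arm couples who start IVF in the window. The IUI-arm rate is 1 - (1 - pIUI)(1 - f × pIVF). Differences are IUI minus IVF in percentage points. With Wilson limits l and u, the Newcombe 95% limits are d - √[(p1-l1)² + (u2-p2)²] and d + √[(u1-p1)² + (p2-l2)²]. Power (normal approximation, two-sided 5%) only indicates how often the interval would exclude zero.

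OHSS 0.5% after IUI and 3% after IVF, 471 per arm:

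| f | IUI-arm rate | Events, IUI vs IVF | Difference (95% CI) | Power |
|---|---|---|---|---|
| 0 | 0.50% | 2 vs 14 | -2.55 (-4.53 to -0.92) | 84% |
| 10% | 0.80% | 4 vs 14 | -2.12 (-4.15 to -0.35) | 70% |
| 25% | 1.25% | 6 vs 14 | -1.70 (-3.77 to +0.20) | 46% |
| 50% | 1.99% | 9 vs 14 | -1.06 (-3.21 to +1.00) | 17% |
| 72% | 2.65% | 12 vs 14 | -0.42 (-2.66 to +1.78) | 6% |
| 82% | 2.95% | 14 vs 14 | 0.00 (-2.29 to +2.29) | 5% |

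The first three rows suit a 270-day window and the last three a 450-day window. The values 72% and 82% are 1 - 0.28 and 1 - 0.18, the success rates in 14.1, if every unsuccessful couple goes on to IVF, as Section 1.1.4 expects. At 1% vs 5%, power for f = 0, 10% and 25% is 95%, 86% and 62%. At 0.5% vs 2% it is 55%, 41% and 24.5%.

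**4. Observation time.** One IVF treatment is watched for 60 days. IUI is watched for 2.700 × 30 = 81 to 2.812 × 30 = 84 days per couple, if the windows do not overlap. As an illustration, an event with the same constant daily rate, 1.0% over 60 days, would appear as 1 - 0.99^(81.0/60) = 1.35% to 1 - 0.99^(84.4/60) = 1.40% under IUI. That is +0.35 to +0.40 points from watch time alone. IUI-arm couples who later have IVF add 60 days each. At f from 50% to 82% the arm average over 450 days is 81 + 0.50 × 60 = 111 to 84.4 + 0.82 × 60 = 134 days, so this effect is then larger.

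**The case against.** The strongest reply has four parts.

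1. Counts by arm are a comparison of rates. The clause is hedged, Section 14.2 calls itself an outline, and tabulating rare harms is common practice. This stands in part. A reader might infer that the trial will produce no comparison of harms, or that the protocol forbids an interval. Neither follows: the counts allow a crude interval, and the wording leaves room to add one. What is missing is a planned estimate.

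2. OHSS is listed by grade, so the yes/no rule does not strictly apply to it. This stands. The splits into any grade and moderate or severe are proposals made here.

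3. The 450-day contrast by allocated group is so diluted by IVF in the IUI arm that an interval around zero could be taken as equal safety. The risk is real, but bare counts of 12 vs 14 invite the same misreading without showing the uncertainty. The answer is to show the dilution by tabulating events by preceding treatment.

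4. The more favourable figures need a 270-day complications window, which Section 8.2.2.1 does not contain. This also stands, so the 270-day result is proposed only as a supplement. Nor can it be assumed free of IVF in the IUI arm. The notes to the schedule in 9.1 bar IVF before day 270, but 7.1.1 offers it after three cycles or 270 days, 15.2 speaks of eight months, and Table 9 allows for further IVF within 270 days.

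**Conclusion.** The mismatch between objective 3 and Section 14.2.2 is confirmed from the text, and it is modest. The objective will receive counts without a planned difference or measure of uncertainty for OHSS, pelvic infection or admission. The primary conclusion, sample size, alpha and margin do not change.

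The size of any harm difference cannot be judged from the protocol. Under the assumed OHSS rates, the interval excludes zero when little IVF occurs in the IUI arm and is centred near zero at high 450-day uptake. All figures use the full 471 per arm. The 10% loss in 14.1 was set for the primary outcome and need not apply to complications recorded about eight weeks after treatment starts.

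The point does not extend to every complication. Multiple and ectopic pregnancy and preterm birth already receive intervals. Obstetric and neonatal events arise only in pregnancies and can stay descriptive.

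**What to change.** Replace the last clause of 14.2.2 with text to this effect:

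*For OHSS (any grade; moderate or severe), pelvic infection and hospital admission (HDU/ITU or standard ward), the number of randomised couples with at least one event in the observation periods of Section 8.2.2.1 will be reported by allocated group, with an unadjusted risk difference and Newcombe 95% CI. These results are exploratory and no significance test will be made. Events will also be tabulated by the treatment that preceded them (IUI or IVF). The same risk difference, restricted to treatment started within 270 days of randomisation, will be given as a supplementary result. The unequal observation time (60 days per IVF treatment, 30 days per IUI cycle) will be stated with the results. Bleeding after oocyte retrieval, obstetric and neonatal events, and other sparse events will be tabulated only.*

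Naming one unadjusted method avoids a choice between methods after the data are seen. No multiplicity change is needed, because secondary outcomes are already exploratory.

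The cost is a few sentences and some table rows, from data on the Post-Treatment form. That form is due 8 weeks (56 days) after stimulation starts, while the IVF period is 60 days, so the trial office should confirm that the last days are captured.

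There are downsides. Intervals will be wide for rare events. The 270-day result leaves out later IUI cycles, which Section 7.1.1 allows up to day 450. The 450-day contrast may sit near zero and must not be read as equal safety of IUI and IVF. Rewording objective 3 as description would align the text but give no estimate.
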